**Suspected Unexpected Serious Adverse Reaction (SUSAR):**

A SUSAR is any unexpected SAE considered as related to the study treatment or to a study specific procedure.

Expected adverse events are those adverse reactions that are listed or characterized in the reference document (e.g., IB).

Unexpected adverse reactions are those not listed in the reference document or not identified. This includes adverse events for which the specificity or severity is not consistent with the description in the reference document.

**8.2.2.2. Time period for collection**

From the date of signature of ICF and up to first TG4050 administration, only serious adverse reactions (SARs) caused by a protocol-required procedure will be collected and reported (refer to section 8.2.2. and 8.2.3). The only protocol-required procedure concerned is the specific blood sample taken during the screening period.

AEs, SAEs, or procedure related ARs that occur between ICF signature and 3 weeks prior to first administration, and that are considered by the investigator as particularly relevant to the patient's condition, will be collected as a current medical history.

If an event occurs during the period from 21 days before and up to first TG4050 administration, it will be recorded either on a "Medical history/current conditions" page for an identified syndrome (e.g., pneumonia) or on a "Signs and symptoms" page for symptoms with no associated syndrome (e.g., diarrhea).

From the first TG4050 administration and in case of worsening of a sign and symptoms which started 21 days before first TG4050 administration, an AE page will be completed using a verbatim starting by "worsening of..."

From the initiation of TG4050 treatment up to the safety follow-up visit (at least 30 days after the last administration of study treatment), all AEs and SAEs should be collected and recorded on the eCRF. During this period all SAEs should also be reported to Transgene.

All SARs related to a study specific procedure occurring during the screening period and all SAEs occurring during the treatment period will be recorded in Transgene safety database.

SAEs occurring more than 30 days after administration of the last dose of TG4050 and evaluated by the investigator as related to TG4050 should be collected and reported to Transgene indefinitely even after study closure. These will however not be reported in the eCRF after Database lock.

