**Efficacy assessment**

- CA-125 determined in an accredited central laboratory will be measured within 7 days prior to treatment initiation and then every 3 weeks throughout the treatment period. CA-125 doubling time and half-life as appropriate, time to normalization and response according to GCIG criteria will be assessed.
- Tumor response will be evaluated by using RECIST 1.1. A CT-Scan of the pelvis and abdomen (or MRI) and X ray or preferably CT-scan of the chest will be performed within 21 days prior to treatment initiation, on Day 43 and then every 9 weeks.

**Immune responses**Patient samples collection:

- Cytapheresis for collection of PBMC will be performed prior to first treatment administration and 9 weeks (D64) after treatment initiation. In case a patient is withdrawn prior to D64, a cytapheresis is to be performed at end of treatment visit. If the post-baseline cytapheresis is not clinically feasible, it can be replaced by a 150 ml blood draw.
- Blood samples (prior to study treatment administration, when applicable) at baseline, on Day 8, Day 22, Day 43, Day 64, Day 85, Day 211 and at the end of treatment visit for extraction of serum, plasma and PBMC for longitudinal monitoring of response.

Blood samples will be collected to assess the following parameters:

- Whole blood cell phenotype on fresh blood samples by multiparametric flow cytometry (FACS). Proposed assessments include counting and phenotyping of memory and naïve T cells, regulatory T cells, CD8 T cells, B cells, NK cells, innate like T cells as well as relevant activation markers
- Quantification of immune related soluble factors, cytokines, antibody responses to neoantigens and virus
- Peripheral Blood Mononuclear Cells (PBMC) from whole blood to assess specific cellular immune responses against neoantigens
- HLA Genotyping (class I and II)
- Circulating tumor and immune markers

Tumor sample(s) will be collected to assess:

- Density of tumor infiltrating lymphocytes (TILs) and phenotyping of the infiltrated cells (cell type and activation markers) (Immunoscoring)
- PD-L1 and other relevant immune related factor expression by IHC assessment
- Transcriptomic analysis of whole tumor and purified immune cell populations
  - Evaluation of tumor mutation load

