### 4.4. Definition of end of study

The end of study is defined as the date of the last patient last visit.

The end of study page in the eCRF will be filled in when patient withdraws the study due to any reason or if the patient dies or progresses. The patient will be considered as completer if she received the 20 injections or progresses or dies or withdraws due to a DLT before the end of treatment.

In addition, the shelf life of TG4050 is 48 months. Considering the planned duration of treatment lasting around 11 months with pre-treatment assessments of around 1 month (confirmation of asymptomatic relapse and baseline visit), patients will need to start treatment at least 12 months before the expiry date. Otherwise, patients will be withdrawn from the trial prior treatment period initiation and their end of study would be defined as the date of study withdrawal.

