### 5.2. Treatment period

At the time of asymptomatic relapse, the patient for whom TG4050 is available will start treatment period. The patient will keep the same identification number for the treatment period. The baseline assessment will last at most 21 days. Tests performed per standard of care (e.g., CT-scan) may not need to be repeated if collected within 28 days prior to start of study treatment.

If the patient is not included for any reason, the reason for non-inclusion and a minimum of other parameters (results of the baseline assessment) will be entered in the eCRF.

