#### 6.2.2. **Baseline visit**

The following procedures will be performed within 21 days prior to treatment start:

- Inclusion/exclusion check
- Physical examination, including vital signs and weight
- PS on ECOG scale
- Current medical conditions and signs/symptoms see section 8.2
- Concomitant medications
- Electrocardiogram
- Tumor assessment by imaging procedures if the previous imaging has been performed more than 4 weeks before treatment start

The following procedures must be performed within 7 days prior to the first dose:

- Inclusion/exclusion check
- Blood analyses including:
  - CBC including RBC, Hb, WBC and differential, platelets
  - Biochemistry tests
  - CA-125 concentration
  - Blood sample and cytapheresis for translational research

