**8.2.2.3. Adverse event / Serious adverse event management****8.2.2.4. Data collection****Reporting in eCRF**

At each visit, all AEs whether volunteered by the patient, discovered by study personnel during questioning, or detected through physical examination, laboratory test, or other means will be reported appropriately on the page "Adverse Events" of the eCRF (= AE page). The following items must be documented:

- nature of the event with self-explanatory and concise medical terminology (if possible indicate a diagnosis or syndrome instead of symptoms),
- date of onset and date of end (i.e. actual dates when the event starts and is resolved rather than dates when the Investigator is informed),
- intensity,
- evaluation of seriousness,
- relation to study treatment or to study procedures,
- action taken regarding the study treatment,
- action taken regarding the event,
- outcome.

AE / AR requiring therapy must be treated with recognized standards of medical care to protect the health and well-being of the patient. Any treatment given will be reported on the page "Concomitant medication" of the eCRF.

Appropriate resuscitation equipment and medicines must be available to ensure the best possible treatment of an emergency situation.

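### Minor: the listing of SAEs before treatment cannot show the undosed patients it is promised for, their deaths have no SAP output, and pre-dose notification omits the mandated baseline cytapheresis

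*Protocol*

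**What the plan says.** **Collection.** For the time between consent and first dose, Protocol 8.2.2.2 gives a general rule, that "only serious adverse reactions (SARs) caused by a protocol-required procedure will be collected and reported", and then its scope: "The only protocol-required procedure concerned is the specific blood sample taken during the screening period". Protocol 8.2.3 puts the same limit on notification to the sponsor. Events in the last 21 days before dose 1 go on a history/current-conditions page or a signs-and-symptoms page. Full AE and SAE collection starts with dose 1.

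**Cytapheresis.** The synopsis says: "Cytapheresis for collection of PBMC will be performed prior to first treatment administration and 9 weeks (D64) after treatment initiation". Protocol 6.2.2 places "Blood sample and cytapheresis for translational research" among the procedures required within 7 days before dose 1, and Appendix II-B agrees. Only the post-baseline procedure may be replaced by a 150 mL blood draw.

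**Outputs.** Protocol 9.4.1 (Adverse events) and SAP 8.10.1.2 promise that pre-treatment SAEs will be listed separately, including those in patients screened and not included. Protocol 9.4.1 (Fatal Events) promises a separate listing of pre-treatment fatal events in such patients. SAP 6.1 defines the SAF by receipt of at least one dose, and SAP 8.10 places all safety analyses in it.

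**The concern.** There are two separate problems.

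The first concerns reporting. A programmer who follows the population label on Listing 16.2.7.3 produces a listing from which the undosed patients are absent by construction. For pre-treatment deaths in undosed patients there is nothing to programme at all.

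The second concerns collection. A site that follows Protocol 8.2.2.2 and 8.2.3 as written would not notify a serious reaction to an invasive procedure that the protocol itself requires before dosing. What is at stake is complete pre-treatment safety reporting in a first-in-man study, not the treatment-emergent results.

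**Working it through.** No figure in the plan needs reproducing, so the check sets the texts side by side.

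**Step 1: promises against outputs.**

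| Promise | Source | SAP output | Population |
|---|---|---|---|
| Pre-treatment SAEs, with patients screened and not included | Protocol 9.4.1; SAP 8.10.1.2 | Listing 16.2.7.3 | SAF (dosed only) |
| Pre-treatment fatal events in patients screened and not included | Protocol 9.4.1 | None | None |

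SAP 8.10.1.2 also names sub-listings for pre-treatment SAEs and for deaths, but gives them no population, so the SAF rule in SAP 8.10 applies. The SAP does use SCR elsewhere, for example in Listings 16.2.1.1, 16.2.6.2 and 16.2.9.1, so no new population is needed.

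**Step 2: is the listing gap empty under the narrow collection rule?** No. A serious reaction to the screening blood sample in a patient who is never dosed is collected under 8.2.2.2 and notified under 8.2.3, but cannot appear in Listing 16.2.7.3.

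**Step 3: where a baseline cytapheresis reaction goes.** The procedure falls within 7 days before dose 1. That is inside the consent-to-dose window and inside the 21-day page rule. It is not the screening blood sample, so 8.2.2.2 and 8.2.3 do not require notification, and the event goes on a history or symptoms page. Protocol 8.2.2.4 specifies seriousness and "relation to study treatment or to study procedures" as items for the AE page. The protocol does not specify them for the other two pages. For a patient never dosed, the 21-day window has no end date to count back from.

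**Step 4: wording that does not fit the limit.**
- Protocol 6.1.1 asks for reports of serious reactions to a protocol-required procedure, with no blood-sample limit.
- The adverse reaction and SUSAR definitions in 8.2.2.1 include study-specific procedures generally.
- The safety-database sentence of 8.2.2.2 takes in "All SARs related to a study specific procedure occurring during the screening period and all SAEs occurring during the treatment period".
- Protocol 5.2 says: "At the time of asymptomatic relapse, the patient for whom TG4050 is available will start treatment period", with the baseline assessment inside that period. Protocol 8.2.3 starts the treatment period at TG4050 initiation. A baseline cytapheresis event is therefore a treatment-period SAE under 5.2 and a screening-period procedure reaction under 8.2.3. The database sentence reaches it on its face either way; the notification rule does not.

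**Step 5: the flow chart.** Appendix II-B marks AE/SAE reporting in the baseline column. The visit list in 6.2.2 has no such item, only current conditions and signs/symptoms, whereas the on-treatment visit lists do name adverse event reporting. The mark is ambiguous.

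**Step 6: size of the data check.** SAP 4 gives 6 treated patients. If each baseline cytapheresis was done within its window, the entries to check in them span at most 6 x 7 = 42 patient-days. Undosed patients who had the procedure would add to this, and their number is not given.

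**The case against.** The best defence of the collection rule is that a general rule followed by its stated scope is not a contradiction, and that 8.2.2.2 and 8.2.3 agree with each other. That stands as a reading of those two sections. It does not explain the wider wording in 6.1.1, in the definitions and in the safety-database sentence, or why a required procedure before dosing is left out.

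On outputs, backstops exist:
- SAP 8.7 allows an adverse event as a reason for failure to treat, and Listings 16.2.6.2 and 16.2.1.1 are on SCR, so an event that prevented dosing can appear there as a reason.
- Narratives are planned for all SAEs, and output 14.3.3 carries no SAF label.
- Protocol 8.2.3 makes the sponsor responsible for reporting all observed AEs and SAEs to the FDA.

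These soften the point, but none is the promised listing.

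A further objection is that relabelling Listing 16.2.7.3 would show little more, because few pre-dose events are collected as SAEs. That is correct, and it shapes the fix.

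A reader might also take Tables 14.3.2.6 (fatal AEs) and 14.3.2.7 (deaths) as failed versions of the pre-treatment death listing. The documents do not support that: both belong to the treatment-period safety section and are correctly on the SAF. The fault is a missing output, not two wrong labels.

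**Conclusion.** Both points hold and both are minor. One listing has a population that cannot hold the patients promised, and one protocol promise has no SAP output. The notification rule leaves out a required pre-dose procedure and does not fit other sections of the protocol.

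Three stronger readings are not supported:
- **That events in most screened patients are lost.** A reader might set the 6 treated against the roughly 60 planned for screening. The number actually screened is not given, and that difference would count people, not events.
- **That cytapheresis reactions go unrecorded.** Protocol 8.2.2.2 sends events in the last 21 days before dosing to history or symptoms pages. What is missing is notification as a serious reaction.
- **That the baseline mark in Appendix II-B proves SAE reporting was intended there.** It may reflect only the history and symptom recording in 6.2.2.

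Pre-dose events are rightly not treatment-emergent, so the TEAE tables and the primary result do not change. The verdict assumes that the output list in SAP 10 is complete.

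**What to change.** 1. **SAP outputs.** Run Listing 16.2.7.3 on SCR, using the item on relation to other study procedures that SAP 8.10.1.2 already specifies. Add an SCR listing of pre-treatment deaths, drawn from the end-of-study page, which Protocol 4.4 requires "when patient withdraws the study due to any reason or if the patient dies or progresses". State both as exceptions to the SAF rule in SAP 8.10.
2. **Check before lock.** Review history and signs/symptoms entries from the baseline cytapheresis to dose 1, or to end of study if undosed, for serious procedure-related events. Query sites where seriousness or causality was not captured, and enter any event found as a pre-treatment SAE. State in the SAP that the pre-treatment listings show only what Protocol 8.2.2.2 collects plus events found in this check.
3. **Protocol, for the record.** Reconcile 8.2.2.2 and 8.2.3 with 6.1.1, 6.2.2, the definitions in 8.2.2.1 and Appendix II-B, so that serious reactions to any protocol-required procedure before first dose are notified. Reconcile 5.2 with 8.2.3 on when the treatment period starts.

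The cost is one population label, one short listing, two sentences in the SAP, and a check of at most 42 patient-days in treated patients (if the procedures were done on time) plus any undosed patients who had the cytapheresis. Some site queries are likely. The study has stopped, so the protocol edits probably affect no further procedure; items 1 and 2 can still act.

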**8.2.2.3. Adverse event / Serious adverse event management****8.2.2.4. Data collection****Reporting in eCRF**

At each visit, all AEs whether volunteered by the patient, discovered by study personnel during questioning, or detected through physical examination, laboratory test, or other means will be reported appropriately on the page "Adverse Events" of the eCRF (= AE page). The following items must be documented:

- nature of the event with self-explanatory and concise medical terminology (if possible indicate a diagnosis or syndrome instead of symptoms),
- date of onset and date of end (i.e. actual dates when the event starts and is resolved rather than dates when the Investigator is informed),
- intensity,
- evaluation of seriousness,
- relation to study treatment or to study procedures,
- action taken regarding the study treatment,
- action taken regarding the event,
- outcome.

AE / AR requiring therapy must be treated with recognized standards of medical care to protect the health and well-being of the patient. Any treatment given will be reported on the page "Concomitant medication" of the eCRF.

Appropriate resuscitation equipment and medicines must be available to ensure the best possible treatment of an emergency situation.

### Intensity

The intensity of AE/SAE will be graded according to the NCI-CTCAE (version 5) which will be provided to the Investigators.

Should an event be missing in the CTCAE, the following 5-point scale is to be used:

- Mild: Discomfort noticed, but no disruption of normal daily activity
- Moderate: Discomfort sufficient to affect normal daily activity
- Severe: Inability to work or perform normal daily activity
- Life-threatening: Risk of death at the time of the event
- Fatal: The patient died

The correspondence between the two scales is as follows:

CTCAE	5-point scale
1	Mild
2	Moderate
3	Severe
4	Life-threatening
5	Fatal

Any increase or decrease in severity category during the course of an adverse event should be reported on the AE pages of the eCRF with corresponding dates.

### Causality

The relationship to IMP of each AE/SAE will be evaluated by the Investigator with EudraVigilance Clinical Trial Module" (EVCTM) method using the following levels:

- **No reasonable possibility** (i.e. no facts (evidence) or arguments to suggest a causal relationship): the temporal relationship of the clinical event to the administration of study

treatments makes a causal relationship unlikely; and other drugs, therapeutic interventions or underlying conditions provide a sufficient explanation for the observed event.

- **Reasonable possibility** (i.e. facts (evidence) or arguments to suggest a causal relationship): the temporal relationship of the clinical event to the administration of the study treatments makes a causal relationship possible; and other drugs, therapeutic interventions or underlying conditions do not provide a sufficient explanation for the observed event. A clear-cut temporal association with improvement on cessation of the study treatment or recurrence upon rechallenge may also be observed.

### Outcome

The outcome is rated as follows:

- recovered,
- not recovered,
- worsening
- recovering,
- recovered with sequelae,
- fatal,
- unknown.

Note on "fatal": this outcome is to be used only for the event leading to death. The outcome of all other events at the time of the death must be reported. The outcome of ongoing ones is reported as "not recovered".

### Action taken regarding the IMP

- None: administration continues as planned in the protocol
- Delayed: administration following the occurrence of the event is delayed
- Cancelled: administration following the occurrence of the event is cancelled
- Stopped: administration is definitively stopped
- Not applicable: administration is already stopped, or study treatment not started yet

### Action taken regarding the event

- New treatment prescribed or change in concomitant medication
- Hospitalization or prolongation of hospitalization
- Non-drug therapy implemented
- None
- Other (to be specified)

#### **8.2.2.5. Follow-up**

Once an AE is detected, it must be proactively followed until its resolution or 30 days after the last study treatment administration.

However, the AEs listed below must be followed until they are resolved or stable or returned to baseline status, which may occur after the safety follow-up visit planned by the protocol:

- AE evaluated as related to the IMP
- SAEs

- Any other significant AE as recommended by Transgene

Transgene or its representative reserves the right to ask for further information on any AE/SAE that may be considered of interest or when the event is not previously documented in the IB (new occurrence) is thought to be related to the IMP.

#### 8.2.2.6. Documentation

All AEs/SAEs will be reported in the source document with at least the nature, the date of onset and end, the causality, and the treatment (if applicable).

Copies of SAE form will be filled in the Investigator Site File along with copies of any correspondence with the Independent Ethics Committee (IEC) / Institutional Review Board (IRB). The Investigator Site File will also include copies of notification letters and/or faxes with forms sent to Health Authorities and Gene Therapy Bodies if appropriate.

#### 8.2.2.7. Notification to investigators

In case of a grade  $\geq 3$  AE suspected to be related to TG4050 occurs, Transgene or its representative will inform all investigators involved in the study that such an event has been reported as soon they became aware.

### 8.2.3. Serious Adverse Event / Serious Adverse Reaction / Suspected Unexpected Serious Adverse Reaction notification

#### Reporting to Transgene

Any SAE occurring during the screening period (after ICF signature and before TG4050 treatment initiation) related to a study specific procedure (specific blood sample taken during the screening period) MUST be reported to Transgene.

Any SAE occurring during the treatment period (from TG4050 treatment initiation and up to 30 days after last study treatment administration) whether or not related to TG4050 MUST be reported to Transgene.

SAEs occurring more than 30 days after administration of the last dose of TG4050 and evaluated by the investigator as related to TG4050 MUST be reported to Transgene.

The Investigator must complete and send (preferably by email otherwise by fax) a "Serious Adverse Event Form" to Transgene within 24 HOURS of occurrence or knowledge of the event.

France	
Pharmacovigilance Physician	
Name	PPD [REDACTED]
Phone number	PPD [REDACTED]
Fax number	PPD [REDACTED]
Email	PPD [REDACTED]
Emergency 24-hour telephone number	PPD [REDACTED]

An Investigator's designee may complete the SAE form; however, the Investigator must sign it. The form can be sent to Transgene with the designee's signature if the Investigator's signature cannot be obtained within one working day. The Investigator's signature must be obtained as soon as possible, as well as his/her evaluation of the relationship to the study treatment. The signed form must be sent (preferably by email otherwise by fax) to Transgene immediately.

The SAE form must be completed in English.

Follow-up information (e.g., complications or progression of the initial SAE) must be notified to Transgene by the Investigator within the same time frame as the occurrence by using a new "SAE form" with the box "follow-up" ticked and sent to the Transgene.

The follow-up information should describe whether the event has resolved or continues, if and how it was treated and whether the patient continued or withdrew his/her consent.

Transgene or its representative may request further information as needed.

All SAEs will be followed to resolution or stabilization.

